In addition, blood samples will be obtained from all participants to measure plasma levels of metopimazine and metopimazine acid following single-dose administration (Day 1) and at steady-state after multiple-dose administration (Week 2). Blood samples for PK will be collected at the Day 1 and Week 2 visits for all participants (up to 3 hours after the first dose on each occasion). In a subset of participants (8 to 10 participants per treatment arm; 32 to 40 participants total), intensive sampling will be performed (up to 6 hours after the first dose at the Day 1 and Week 2 visits, as well as 1 and 2 hours after the second dose at the Day 1 visit).

Disclosure Statement:

This is a parallel group treatment study with 4 arms that is participant, investigator, and sponsor blinded.

Number of Participants:

A total of approximately 280 participants will be randomized to achieve an estimated 224 participants completing the 12-week Treatment Period (and approximately 56 participants per treatment arm). At least 120 randomized participants will have diabetic gastroparesis and at least 120 randomized participants will have idiopathic gastroparesis. Up to approximately 140 participants can be cannabinoid users, and of these, up to approximately 56 can be marijuana users.

Intervention Groups and Duration:

The total duration of the study for each participant will be approximately 20 weeks.

On Day 1 of the Treatment Period, eligible participants will be randomized in a 1:1:1:1 ratio to receive either NG101 5 mg, 10 mg, or 20 mg, or matching placebo. Study drug will be administered orally 4 times per day (QID) for 12 weeks. The 20 mg arm will initiate dosing on

Day 1 with 5 mg QID for 4 days, followed by 10 mg QID for 3 days, and then 20 mg QID through Week 12. No titration will occur in the 5 mg and 10 mg arms.

[figure not shown]
The study drug should be taken by participants approximately 30 minutes before a meal 3 times a day and 30 minutes before bedtime, with a minimum interval of 4 hours between doses.

Data Monitoring Committee and Data Safety Monitoring Board:

A Data Monitoring Committee (DMC) comprised of representatives from the sponsor and CRO will review blinded data on an ongoing basis.

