Study medication											
4 × per day (QID) The study drug should be taken approximately 30 minutes before a meal 3 times a day and 30 minutes before bedtime, with a minimum interval of 4 hours between doses.
 
Day 1: first dose in clinic, and second dose in clinic for Intense PK subset
 
Week 1: a dose in clinic
 
Week 2: first dose of the day in clinic
 
Week 12: a dose in clinic
 
See Section 6.1.
						
Healthcare resource utilization											See Section 8.12 .						
AE / SAE review											See Section 8.5 .						
Concomitant medication review											Including cannabinoid use						

Procedure	Screening Visit	Pre-treatment Visit	Treatment Period Visits						E/D Visit	EoS / Follow-up Visit	Notes	
	(up to 28 days before Day -14)	Day	Day	Week				-17 to -14	(14 ± 3 days after last dose)			
		1 (± 2d)	2 (± 2d)	4 (± 2d)	8 (± 3d)	12 (± 3d)						
DIGS-DD and Gastroparesis additional daily assessments											Completed once daily at the same time each day. Compliance with completion of the daily diary will be assessed at each visit.	
PGI-S, PGI-C and Treatment Satisfaction Assessment											Completed once weekly on the 7 th day of the week. PGI-C and Treatment Satisfaction will be completed after Day 1	
GCSI-DD assessment		X						X*			The GCSI-DD is completed once daily during the Pretreatment Period, and *daily during the last week of the Treatment Period (participant will receive the GCSI-DD beginning the day after completing the Week 11 PRO's).	
PAGI-SYM, PAGI-QOL, Nausea Profile,			X		X	X	X	X	X	X	At relevant visits, these assessments should be completed first before any other assessments/examinations are completed.	
Nausea Improvement Assessment								X	X		Completed once at the end of the study.	

Procedure	Screening Visit	Pre-treatment Visit	Treatment Period Visits						E/D Visit	EoS / Follow-up Visit (14 ± 3 days after last dose)	Notes	
	(up to 28 days before Day -14)	Day	Day	Week								
		-17 to -14	1	(± 2d)	2	(± 2d)	4	(± 2d)	8	(± 3d)	12	(± 3d)
Blood sample(s) for plasma drug concentration			X		X							

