5.3.1. Meals and Dietary Restrictions

Refrain from consumption of Seville oranges, grapefruit or grapefruit juice for a minimum of 7 days prior to starting study drug until after the final dose.

The study drug should be taken by participants approximately 30 minutes before a meal 3 times a day and 30 minutes before bedtime, with a minimum interval of 4 hours between doses.

Day 1 and Week 2 Visits:

For the Day 1 and Week 2 PK assessments, participants who are not in the Intensive PK Subset should arrive at the clinic in the morning after fasting (water is allowed) for at least 4 hours, and either prior to taking any study drug or within 4 to 6 hours after the first dose of study drug of the day. (See also [Section 8.7.1.](#))

For the Day 1 and Week 2 PK assessments in the Intensive PK Subset, participants should arrive at the clinic in the morning after fasting (water is allowed) for at least 8 hours and prior to the first dose of study drug of the day. (See also [Section 8.7.1.](#))

At the Day 1 and Week 2 visits, study drug should be administered in the clinic approximately 30 minutes before eating. The first dose should be administered with 240 mL of water. No additional water is permitted until 30 minutes after dosing, after which time, water is allowed ad libitum.

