6.1. Study Drug(s) Administered

The study drugs planned for use are described in [Table 1](#) below:

Table 1: Study Drugs

Arm Name	NG101 5 mg Arm	NG101 10 mg Arm	NG101 20 mg Arm	Placebo Arm
Intervention Name	Metopimazine mesylate	Metopimazine mesylate	Metopimazine mesylate	Placebo
Type	Drug	Drug	Drug	Placebo
Dose Formulation	Capsule	Capsule	Capsule	Capsule
Dosage Level(s)	NG101 5 mg, QID	NG101 10 mg, QID	NG101 20 mg, QID	Placebo, QID
Route of Administration	Oral	Oral	Oral	Oral
Use	Experimental	Experimental	Experimental	Placebo comparator
IMP and NIMP	IMP	IMP	IMP	NIMP
Sourcing	Provided by the sponsor	Provided by the sponsor	Provided by the sponsor	Provided by the sponsor
Packaging and Labeling	NG101 5 mg capsules will be provided in a blister pack labeled as required per country requirement	NG101 10 mg capsules will be provided in a blister pack labeled as required per country requirement	NG101 20 mg capsules will be provided in a blister pack labeled as required per country requirement	Placebo capsules will be provided in a blister pack labeled as required per country requirement

Study drug will be dispensed at each visit during the Treatment Period. Each participant will also be dispensed an extra blister pack in case dispensed study drug becomes depleted. Participants will be required to return for clinic visits with all dispensed medication (ie, study drug and rescue medication) to ensure use is recorded properly. Note that during the following visits, study drug will be administered in the clinic:

- **Day 1:** first dose in the clinic, and second dose of the day in the clinic for those participants in the Intense PK subset
- **Week 1:** a dose in the clinic (ie, not necessarily the first dose of the day)
- **Week 2:** first dose of the day in the clinic
- **Week 12:** a dose in the clinic (ie, not necessarily the first dose of the day)

All study drug capsules will be identical in appearance in order to maintain the blind.

Participants in the 20 mg treatment arm will be titrated up to the target dose in a blinded fashion. Specifically, the 20 mg arm initiation blister pack will contain a 4-day supply of 5 mg QID, and a 3-day supply of 10 mg QID, after which the blister packs will contain a 7-day supply of 20 mg QID. (Note: For participants in the placebo, 5 mg, or 10 mg arms, the blister pack will contain only the assigned treatment doses.)

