6.4. Study Compliance

Compliance with completing study visits and assessments per protocol will be assessed throughout the study.

Compliance with completing daily diaries during the Pretreatment Period and the Treatment Period will also be assessed.

When participants are dosed at the site (Day 1, Week 1 and Week 2), they will receive study drug under medical supervision. The date and time of each dose administered in the clinic will be recorded in the source documents and recorded in the CRF.

Compliance with study drug will be assessed at each visit. Compliance will be assessed by counting returned capsules during the site visits and documented in the source documents and CRF. Deviation(s) from the prescribed dosage regimen should be recorded in the eCRF. A record of the number of capsules dispensed to and taken by each participant must be maintained and reconciled with study drug and compliance records. Intervention start and stop dates, including dates for intervention delays and/or dose reductions will also be recorded in the CRF.

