8.7.1. Pharmacokinetic Assessment Methods and Timing

All participants will participate in PK assessment. A subset of participants who consent will participate in intensive PK sampling. The timing of blood sample collections is provided in [Table 4](#) below.

At the Day 1 and Week 2 visits, participants should arrive at the clinic after fasting (see [Section 5.3.1](#) for further details). Participants may have water during the fasting period, but no food should be consumed. Study drug should be taken 30 minutes before eating, at which point 240 mL of water should be provided with the dose. No additional water is permitted until 30 minutes after dosing, after which time, water is allowed ad libitum and a meal will be consumed.

Table 4: Pharmacokinetic Sampling Times

Study Day	Sparse PK		Intensive PK Subset
	PK Sample Timepoint (Hours after dose) (± Time window)	PK Sample Timepoint (Hours after dose) (± Time window)	PK Sample Timepoint (Hours after dose) (± Time window)
Day 1	Predose ^a		Predose ^a
	--		0.5 hours (± 5 minutes)
	1 hour (± 5 minutes)		1 hour (± 5 minutes)
	--		1.5 hours (± 5 minutes)
	2 hours (± 10 minutes)		2 hours (± 10 minutes)
	3 hours (± 10 minutes)		3 hours (± 10 minutes)
	--		4 hours (± 10 minutes)
	--		5 hours (± 10 minutes)
	--		6 hours (± 10 minutes)
	--	Administer second dose	
	--		1 hour (± 5 minutes)
	--		2 hours (± 10 minutes)
Week 2	Predose ^a		Predose ^a
	--		0.5 hour (± 5 minutes)
	1 hour (± 5 minutes)		1 hour (± 5 minutes)
	--		1.5 hours (± 5 minutes)
	2 hours (± 10 minutes)		2 hours (± 10 minutes)
	3 hours (± 10 minutes)		3 hours (± 10 minutes)
	--		4 hours (± 10 minutes)
	--		5 hours (± 10 minutes)
	--		6 hours (± 10 minutes)

Abbreviations: PK = pharmacokinetic

^a Within 15 to 20 minutes before dosing.

Note: For the Week 2 assessment in the Sparse PK group, participants should arrive at the clinic in the morning after fasting for at least 4 hours, and either prior to taking any study drug or within 4 to 6 hours after the first dose of study drug of the day.

Note: For the Week 2 assessment in the Intensive PK group, participants should arrive at the clinic in the morning after fasting for at least 8 hours and prior to the first dose of study drug of the day.

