8.7.1.1. Blood Sample Assessment

Venous blood samples (6 mL) for the determination of plasma concentrations of metopimazine and metabolite (metopimazine acid) will be drawn by direct venipuncture or via an IV catheter into K2 EDTA Vacutainer[®] tubes at the times indicated in Table 4. Additional information regarding blood collection and sample preparation are provided in the Laboratory Manual.

Drug concentration information will be masked prior to database lock since these parameters have the potential to unblind a participant's dose group.

Sample handling and labelling

Each aliquot of plasma will be identified as follows:

- Line 1: **Study NG101-201**
- Line 2: randomization number,
- Line 3: Study Day (ie, Day 1 or Week 2) and time since the first dose administered in clinic on that day.
- Line 4: Plasma PK assay, Aliquot number

Sample Shipment and Storage

The samples will be shipped in a container filled with enough dry ice to ensure that the samples are kept frozen.

The study samples will be shipped to the Sample Custodian as defined in the Lab Manual.

Bioanalytical Method

Plasma concentrations of metopimazine and metopimazine acid will be measured by [REDACTED]
[REDACTED]. using a fully validated method.

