8.8. Pharmacodynamics

Inhibition of dopamine receptors is associated with an increase in serum prolactin levels. This is because dopamine has an inhibitory effect on the anterior pituitary lactotrophs which secrete prolactin. Thus, prolactin levels will be measured in this study (as indicated in [Table 5](#)) to characterize the pharmacodynamic effects of NG101. Blood samples for serum prolactin assessment will be sent to the central laboratory [REDACTED]. Results of prolactin level measurements after the pre-dose assessment on Day 1 will remain blinded until database lock.

Note that during the following visits, study drug will be administered in the clinic:

- **Day 1:** first dose in the clinic, and second dose of the day in the clinic for those participants in the Intense PK subset
- **Week 1:** a dose in the clinic (ie, not necessarily the first dose of the day)
- **Week 2:** first dose of the day in the clinic
- **Week 12:** a dose in the clinic (ie, not necessarily the first dose of the day)

Table 5: Serum Prolactin Sampling Times

Study Day	All Participants (\pm Time window)	Intensive PK Subset (\pm Time window)
Screening Visit	Screening Visit	Screening Visit
Day 1	Predose ^a 1 hour (\pm 5 minutes) -- -- --	Predose ^a 1 hour (\pm 5 minutes) 2 hours (\pm 5 minutes) 3 hours (\pm 10 minutes) 6 hours (\pm 10 minutes)
Week 2 Visit	Predose ^a 1 hour (\pm 5 minutes) -- -- --	Predose ^a 1 hour (\pm 5 minutes) 2 hours (\pm 10 minutes) 3 hours (\pm 10 minutes) 6 hours (\pm 10 minutes)
Week 12 or E/D Visit	Predose ^a 1 hour (\pm 5 minutes)	Predose ^a 1 hour (\pm 5 minutes)
EoS / Follow-up Visit	EoS / Follow-up Visit	EoS / Follow-up Visit

Abbreviations: E/D = Early discontinuation; EoS = End of study; PK = pharmacokinetic

^a Within 15 to 20 minutes before dosing.

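### The protocol gives two incompatible Week 2 dosing rules for sparse-PK participants, and no visible passage requires the time of an earlier home dose, so predose PK and prolactin samples may mix different times since last dose

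*Combined protocol and SAP*

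**What the plan says.** **Week 2 dose.** Section 6.1 sets the Week 2 dose as "first dose of the day in the clinic". Section 8.8 repeats this just above the prolactin sampling table, and the Schedule of Activities (Section 1.3) agrees: "first dose of the day in clinic". None of the three makes an exception for sparse-PK participants. The Synopsis times PK sampling for everyone "up to 3 hours after the first dose on each occasion".

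**Week 2 arrival.** The note to Table 4 (Section 8.7.1) has sparse-PK participants come in the morning after a fast of 4 hours or more. On dosing before arrival it reads: "either prior to taking any study drug or within 4 to 6 hours after the first dose of study drug of the day". Section 5.3.1 gives the same option and extends it to Day 1: "For the Day 1 and Week 2 PK assessments, participants who are not in the Intensive PK Subset should arrive at the clinic". The Intensive PK subset must arrive before its first dose.

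**Recorded times.** Section 6.4 states: "The date and time of each dose administered in the clinic will be recorded in the source documents" and in the CRF. Other dosing is checked by counting returned capsules. PK aliquots are labelled with "time since the first dose administered in clinic on that day" (Section 8.7.1.1). In Tables 4 and 5, predose means 15 to 20 minutes before dosing.

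**Week 12.** Sections 6.1 and 8.8 both allow any dose of the day to be the clinic dose, and a predose prolactin sample is taken at that visit.

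**The concern.** A participant who takes the first dose at home and arrives 4 to 6 hours later receives a later dose in the clinic. That complies with Sections 5.3.1 and 8.7.1 and breaches Sections 1.3, 6.1 and 8.8. Sites have no basis in the text for choosing between the two, and different sites may choose differently.

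The word predose would then cover two quantities: an overnight trough in participants who arrive undosed, and a value a few hours after a dose in the others. The sample label does not separate them, because it counts from the clinic dose. The home dose also carries over into the 1- to 3-hour samples.

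PK parameters and change in prolactin are secondary endpoints (Section 9.3.4). PK also feeds the exploratory associations with symptom scores and safety (Section 9.3.5). A separate PK Analysis Plan can adjust for time since last dose only if that time was collected.

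**Working it through.** The protocol states no figure on this point, so there is nothing to reproduce. The check compares the text and then sizes the consequence.

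**1. The rules side by side (Week 2, sparse-PK group)**

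| Source | First dose of the day | Clinic dose |
|---|---|---|
| Sections 1.3, 6.1, 8.8 | in clinic | is the first dose |
| Sections 5.3.1, 8.7.1, option A | not yet taken on arrival | is the first dose |
| Sections 5.3.1, 8.7.1, option B | taken 4 to 6 h before arrival | is not the first dose |

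Option A agrees with the first row. Option B cannot. On Day 1, option B is empty, because Section 6.1 gives the first dose ever in the clinic.

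**2. Who is covered.** The Intensive PK subset is 32 to 40 participants of about 280 randomized. The sparse group is 280 − 40 = 240 to 280 − 32 = 248. With 70 per arm and 8 to 10 intensive participants per arm, 60 to 62 per arm are sparse, so 180 to 186 of these are on active drug.

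**3. Size for metopimazine.** Inputs:
- Half-life h = 2 to 2.3 h (Section 2.2.1.1).
- Home dose 4 to 6 h earlier (option B).
- Bedtime dose 8 to 10 h earlier (option A). This is an assumption; the protocol gives only a 4-hour minimum interval between doses.

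The share remaining is 2^(−t/h), ignoring carry-over from still earlier doses:

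| t (h) | h = 2 | h = 2.3 |
|---|---|---|
| 4 | 25% | 30% |
| 6 | 12.5% | 16% |
| 8 | 6.3% | 9.0% |
| 10 | 3.1% | 4.9% |

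The ratio between routes is 2^(gap/h). The two windows allow gaps from 8 − 6 = 2 h to 10 − 4 = 6 h:
- smallest: 2^(2/2.3) = 1.8
- largest: 2^(6/2) = 8
- at a gap of exactly 4 h: 2^(4/2.3) = 3.3 to 2^(4/2) = 4

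**4. Sensitivity to half-life.** One-compartment accumulation at 6-hourly dosing is 1/(1 − 2^(−6/h)), which is 1.14 to 1.20 for h = 2 to 2.3. Section 2.2.1.1 reports 30 to 40%. Solving for 1.3 and 1.4 gives an effective h of 2.84 and 3.32 h. The ratio is then 2^(2/3.32) = 1.5 to 2^(6/2.84) = 4.3.

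For metopimazine acid, h = 2.7 to 3.5 h gives 2^(2/3.5) = 1.5 to 2^(6/2.7) = 4.7. The acid's stated AUC accumulation of 1.7 to 1.9 implies h of 4.69 to 5.57 h, which gives 2^(2/5.57) = 1.3 to 2^(6/4.69) = 2.4.

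**5. Can these levels be measured?** Mean Cmax was 20.6 ng/mL at 15 mg, and the phase 1 quantification limit was 5 ng/mL (Section 2.2.1.2). Scaling in proportion to dose gives a Cmax of 6.9, 13.7 and 27.5 ng/mL at 5, 10 and 20 mg. Counting decay from 1 hour after the dose, 2^(−(t−1)/h), 18 to 40% remains at 4 to 6 h and 4 to 12% at 8 to 10 h. At 4 to 6 h this is about 1.2 to 2.8, 2.4 to 5.6 and 4.9 to 11.1 ng/mL at the three doses. At 8 to 10 h even the 20 mg dose gives only 1.2 to 3.3 ng/mL. The assay limit for this study is not given.

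**6. Prolactin.** The protocol gives no time course of prolactin after a dose, so no figure can be derived.

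**The case against.** **Use of the option may be limited.** Arrival must be in the morning, after a 4-hour fast, and doses precede meals by about 30 minutes. A participant who dosed and ate at home could arrive no earlier than about 4.5 hours after the dose. For arrival by noon, the home dose would be at about 07:30 or before. PRO, ECG and vital-sign assessments come before blood draws, which lengthens the interval further. This stands: it makes the 8-fold end less likely, and 240 to 248 counts the people offered the option, not its users. The contradiction remains.

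**Low levels may be unmeasurable.** At 5 mg, and mostly at 10 mg, both routes fall below the phase 1 limit. This also stands, so the ratio may be observable mainly at 20 mg unless the assay is more sensitive.

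**Home-dose times may be collected elsewhere.** A reader might infer that they are not recorded. The documents do not establish that. The CRF, Laboratory Manual and PK Analysis Plan are not supplied, the diary content in Appendix 10.4 is not shown, and a site applying option B would have to ask about the first dose. The text supports only that no visible passage requires the time.

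**Week 12.** A reader might see a second contradiction here. There is none: Sections 6.1 and 8.8 agree that the Week 12 dose is "a dose in the clinic (ie, not necessarily the first dose of the day". Nor does it matter that Section 6.4 names only Day 1 and Weeks 1 and 2 as site-dosing visits, because its recording sentence covers every clinic dose. What remains at Week 12 is an undefined interval since the previous dose before the predose prolactin sample.

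**Day 1.** The extension to Day 1 is a drafting error with no effect on data.

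**Conclusion.** The concern holds as an internal contradiction. The Week 2 clinic dose cannot be the first dose of the day for everyone and also follow a home dose in some sparse-PK participants. If sites use the permitted option, Week 2 predose samples mix times since last dose, and no visible passage requires the information needed to separate them.

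For metopimazine the two routes would differ about 1.8- to 8-fold, or 1.5- to 4.3-fold with a half-life that matches the reported accumulation. Both ranges rest on the assumed 8 to 10 hours since a bedtime dose. The narrower 3.3- to 4-fold figure applies only if the gap between routes is exactly 4 hours, which the protocol does not fix.

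A reader might also infer that prolactin is distorted in proportion to dose. Without a prolactin time course, neither the size nor the pattern of any distortion can be stated.

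The Intensive PK subset is unaffected by the Week 2 conflict. The issue reaches the secondary PK and prolactin endpoints and the exploratory exposure-response analyses. It does not touch the primary nausea endpoint. It should be corrected.

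**What to change.** 1. Reconcile Sections 1.3, 5.3.1 (including its Day 1 wording), 6.1, 8.7.1 and 8.8 to one consistent Week 2 rule. Which rule to adopt is for the sponsor; this review does not choose.
2. Require in the protocol and CRF the date and clock time of the last dose taken, at home or in clinic, before each predose PK and prolactin sample at Week 2 and before the predose prolactin sample at Week 12. If the CRF already has this field, it is enough to say so in Section 6.4.
3. Use time since last dose in the PK model and in the prolactin summaries.

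The cost is a wording change, one CRF field and a small site burden. No extra samples or visits are needed.

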8.7.1.1. Blood Sample Assessment

Venous blood samples (6 mL) for the determination of plasma concentrations of metopimazine and metabolite (metopimazine acid) will be drawn by direct venipuncture or via an IV catheter into K2 EDTA Vacutainer[®] tubes at the times indicated in Table 4. Additional information regarding blood collection and sample preparation are provided in the Laboratory Manual.

Drug concentration information will be masked prior to database lock since these parameters have the potential to unblind a participant's dose group.

Sample handling and labelling

Each aliquot of plasma will be identified as follows:

- Line 1: **Study NG101-201**
- Line 2: randomization number,
- Line 3: Study Day (ie, Day 1 or Week 2) and time since the first dose administered in clinic on that day.
- Line 4: Plasma PK assay, Aliquot number

Sample Shipment and Storage

The samples will be shipped in a container filled with enough dry ice to ensure that the samples are kept frozen.

The study samples will be shipped to the Sample Custodian as defined in the Lab Manual.

Bioanalytical Method

Plasma concentrations of metopimazine and metopimazine acid will be measured by [REDACTED]
[REDACTED]. using a fully validated method.

